2.5 Secondary endpoints

- disease free survival
- overall survival

2.6 Exploratory endpoints:

- prognostic value of tumor shrinkage
- prognostic value of inflammatory infiltrates in and around the resected tumor
- serum- and tumor tissue cytokine concentrations
- multi-OMICS tissue analysis approach for markers and mechanisms

3 Overview of Study Design and Dosing Regimen

The study is designed as an open-label, single arm, prospective, monocentric, phase II study of pembrolizumab in a neoadjuvant setting in patients with non-small cell lung cancer of Stage II/IIIA suitable for surgery.

During the treatment phase, patients will receive intravenous pembrolizumab 200 mg q3wks. for 2 cycles or occurrence of non-tolerable toxicity. After completion of immunotherapy lobectomy or bilobectomy with curative intent is scheduled. After end of protocol treatment, patients will be treated individually according to local standards.

3.1 Treatment Phase

After screening, patients will be treated with Pembrolizumab every 3 weeks for 2 cycles. A non-invasive tumor assessment by PET-CT will be performed before neoadjuvant treatment and before curative intent surgery. If tumor progression or non-tolerable toxicity is noted during immunotherapy, an End of Treatment (EOT) visit will be performed and the patient will enter the follow-up phase.

3.1.1 Surgery

Surgery is the standard treatment in the neoadjuvant treatment approach and not a study specific procedure. The procedure of standard lobectomy/bilobectomy with systematic lymph-node dissection is well described in all manuals of thoracic surgery. In brief, patients undergo general anaesthesia and endobronchial double-lumen intubation. Blood pressure, heart rate, electrocardiographic trace, respiratory frequency and oxygen saturation are monitored continuously throughout the operation by an anaesthesiologist. Thoracotomy is usually performed through the fourth or fifth intercostal space. Vascular and bronchial structures at the level of the hilum are prepared and resected along with the corresponding lobe and lymph node containing fatty tissues. A radical systematic lymph node dissection accomplishes a standard lobectomy procedure. Vessels can be closed by ligation, suture or stapler. The bronchus can be closed by suture or stapler. Depending on the anatomical consideration of the interlobar fissure and the different techniques in use, the division can be performed at the beginning or the end of the surgery and can be done by

stapler, cautery or any other technique. Surgical technique for closure of vessels and bronchus, and the different techniques of parenchymal sparing have to be described for each patient in the OP-records. In special cases video-assisted thoracic surgery (minimal-invasive; small incisions) may replace open thoracotomy (larger incision). Two standard chest tubes are placed at the end of the operation. Postoperative patients will be monitored on the intensive care unit for at least 12 hours.

3.2 End of Treatment

End of Treatment is defined as 6 weeks post surgery (approx. 4 weeks post discharge). In patients who discontinue during the treatment phase, an End of Treatment (EOT) visit will be performed within 28 days after treatment discontinuation.

3.3 Follow-up Phase

After treatment discontinuation, follow-up evaluations will be performed every 3 months in order to collect information on relapse, survival status and subsequent cancer treatment until end of study.

3.4 End of Study

All enrolled patients will be followed up until the end of the study. The study will be terminated as soon as the last patient has completed at least 24 months of follow-up.

3.5 Assignment of Patients to Treatment

A total of 30 patients will be enrolled into the study and will receive neoadjuvant treatment of 2 cycles of pembrolizumab.

3.6 Study sites

The study will be conducted in one center only, which will recruit all required patients.

3.7 Study Duration

Study duration is approximately 64 months measured from FPI.

AIO-Studien-gGmbH

FPIQ2/2018LPIafter approx. 36 monthLPOafter approx. 40 monthEoS (after 24 month FU of LPO)after approx. 64 month

4 Selection of the Study Population

4.1 Target Population

Patients with resectable NSCLC stage II/IIIA eligible for immunotherapy and surgery.

4.2 Inclusion Criteria

- 1. Cooperation and willingness to complete all aspects of the study
- 2. Signed and dated written informed consent must be given prior to study inclusion
- 3. Histological or cytological confirmed NSCLC
- 4. Clinical stage II-IIIA according to the TNM classification, 7th edition: stage IIIa: T1/T2 N2 (IIIa₁₋₃ Robinson classification)
- 5. Adequate disease staging by PET/CT and brain MRI
- 6. At least 1 measurable lesion according to RECIST 1.1
- 7. Age \geq 18 years
- 8. ECOG performance status 0 1
- Female subjects of childbearing potential (Section 7.6.6) must be willing to use an adequate method of contraception as outlined in Section 7.6.6 – Contraception and Pregnancy, for the course of the study through 120 days after the last dose of study medication.

Note: Abstinence is acceptable if this is the usual lifestyle and preferred contraception for the subject.

Female subject of childbearing potential should have a negative urine or serum pregnancy within 72 hours prior to receiving the first dose of study medication. If the urine test is positive or cannot be confirmed as negative, a serum pregnancy test will be required.

10. Male subjects of childbearing potential (Section 7.6.6) must agree to use an adequate method of contraception as outlined in Section 7.6.6 – Contraception and Pregnancy, starting with the first dose of study therapy through 120 days after the last dose of study therapy.

Note: Abstinence is acceptable if this is the usual lifestyle and preferred contraception for the subject.

- 11. Adequate bone marrow function, liver and renal function:
 - a. Absolute neutrophil count $\ge 1.5 \times 10^9$ /L
 - b. Thrombocytes \geq 100 x 10⁹/L
 - c. Hemoglobin ≥ 9 g/dL without transfusion or EPO dependency (within 7 days of assessment)
 - INR < 1.4 ULN and PTT < 40 seconds during the last 7 days before therapy
 - e. Bilirubin < 1.5 x upper limit of normal
 - f. AST (GOT) and ALT (GPT) < 2.5 x ULN
 - g. Albumin >2.5 mg/dL
 - h. Serum creatinine **OR** Measured or calculated creatinine clearance (GFR can also be used in place of creatinine or CrCl):

≤1.5 X upper limit of normal (ULN) OR

≥60 mL/min for subject with creatinine levels > 1.5 X institutional ULN

12. Adequate lung and cardiac function for intended lung resection according to German S3 guideline

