	setting in patients with non-small cell lung cancer of Stage II/IIIA		
	suitable for curative intent surgery		
Indication	Resectable NSCLC stage II/IIIA		
Proposed countries /	Germany		
Total number of sites	Number of sites total: 1		
Primary objective	To assess feasibility and safety of a neoadjuvant application of		
	pembrolizumab		
	To assess antitumor activity of pembrolizumab with regard to		
	clinical and pathologic tumor response		
Secondary objectives	To assess the impact of neoadjuvant pembrolizumab on patient		
	disease free and overall survival.		
Exploratory	To explore potential predictive biomarkers for pembrolizumab		
objectives	efficacy		
	Immune cell imaging:		
	 immune cell infiltrates in and around the resected tumor 		
	 tumor tissue- and serum cytokine profiles 		
	 Hypothesis generation on potential biomarkers predicting efficacy of pembrolizumab using multi-OMICS analysis 		
Planned sample size	N=30.		

Inclusion criteria	1. Cooperation and willingness to complete all aspects of the
	study
	2. Signed and dated written informed consent must be given prior to study inclusion
	3. Histological or cytological confirmed NSCLC.
	4. Clinical stage II-IIIA according to the TNM classification, 7th
	edition.
	stage IIIa: T1/T2 N2 (IIIa ₁₋₃ Robinson classification)
	5. Adequate disease staging by PET/CT performed and
	resectability established.
	6. At least 1 measurable lesion according to RECIST 1.1
	7. Age ≥ 18 years
	8. ECOG performance status 0 - 1
	9. Female subjects of childbearing potential must be willing to use
	an adequate method of contraception as outlined in in the
	protocol, for the course of the study through 120 days after the
	last dose of study medication.
	Note: Abstinence is acceptable if this is the usual lifestyle and
	preferred contraception for the subject.
	Female subject of childbearing potential should have a
	negative urine or serum pregnancy within 72 hours prior to
	receiving the first dose of study medication. If the urine test is
	positive or cannot be confirmed as negative, a serum
	pregnancy test will be required.
	10. Male subjects of childbearing potential must agree to use an
	adequate method of contraception as outlined in protocol,
	starting with the first dose of study therapy through 120 days
	after the last dose of study therapy.
	Note: Abstinence is acceptable if this is the usual lifestyle and
	preferred contraception for the subject.
	11. Adequate bone marrow function, liver and renal function:

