	The degree of the potential evidence provided by a sample size of
	N=30 is summarized in the statistics section of the protocol.
Endpoints / Statistical	The trial design will be a phase II trial, with descriptive outcome
analysis	assessments of:
	Primary endpoints:
	 frequency and severity of adverse events including peri-
	and post-operative complications (grade 2-4 AEs
	according to NCI-CTCAE V4.03)
	 number of patients treated in compliance with
	protocol
	Tumor response evaluation
	Clinical response parameters:
	Clinical response parameters: \circ response rates (Δ tumor size / lymph node size),
	 Clinical response parameters: o response rates (∆ tumor size / lymph node size), according to RECIST 1.1 criteria
	 Clinical response parameters: o response rates (∆ tumor size / lymph node size), according to RECIST 1.1 criteria o ∆ PET-activity (standardized uptake value [SUV])
	 Clinical response parameters: o response rates (∆ tumor size / lymph node size), according to RECIST 1.1 criteria
	 Clinical response parameters: o response rates (∆ tumor size / lymph node size), according to RECIST 1.1 criteria o ∆ PET-activity (standardized uptake value [SUV])

	Secondary endpoints:disease free survivaloverall survival	
Study plan	FPI	Q2/2018
	LPI	after approx. 36 month (Q2/2021)
	LPO	after approx. 40 month
		(Q4/2021)
	EoS (after 24 month FU of LPO)	after approx. 64 month
		(Q4/2023)

Schedule of Study Assessments

Study Phase	Screening	Treatme	Treatment phase		Dis-charge	End of treatment	Follow-up
Procedure	SCR	V1	V2	PS	D	EOT	FU1 – FUx
Time windows	Day - 28	Day 1	V2 Day 21 +/- 3 days	Day 43-50	Day 60-74	6 wks. after	every 3
	to 0	Day I	Day 21 +/- 5 uays	Day 43-50	Day 00-74	surgery	months
Informed consent	 					Surgery	monting
Demographics	X X						
(age, gender, race)							
Tumor diagnosis	Х						
Cancer history	Х						
Medical history (incl. smoking status)	Х						
Previous treatments	X						
Tumor assessments (PET)-CT, RECIST 1.1	Х			Х			
Tumor staging (PET-CT, MRI brain)	Х						
Chest X-ray	Х		Х	Х	Х	Х	
Cardiac evaluation (12-lead ECG)	Х		(X) ¹	Х		Х	
Physical examination ²	Х		Х	Х	Х	Х	
Body weight and height / BSA ³	Х		Х	Х		Х	
Vital signs (BP, HR, body temperature)	Х	(X) ⁸	х	Х	х	х	
Lung function test blood gas values	Х		х	х		х	
ECOG status	Х		Х	Х		Х	
Pregnancy test (if applicable)	Х	(X) ⁸					
Hematology ⁴	Х	(X) ⁸	Х	Х	Х	Х	
Coagulation	Х	(X) ⁸	Х	Х	Х	Х	
Clinical chemistry ⁵	Х	(X) ⁸	Х	Х	Х	Х	
tumor marker	Х			Х		Х	
TSH ⁶	Х		Х	Х	Х	Х	

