In- / Exclusion criteria	Х						
Biomarkers (blood sample)		Х	Х	Х	Х	Х	
Tumor tissue ⁹	Х				Х		
HR-QoL	Х			Х		Х	
Treatment (V1/V2)		Pembrolizumab 200 mg i.v	Pembrolizumab 200 mg i.v				

0316-ASG / NEOMUN

Study Phase Procedure	Screening	Treatment phase		Pre- Surgery	Dis-charge	End of treatment	Follow-up
Visit	SCR	V1	V2	PS	D	EOT	FU1 – FUx
Time windows	Day - 28 to 0	Day 1	Day 21 +/- 3 days	Day 43-50	Day 60-74	6 wks. after surgery	every 3 months
Concomitant medication	Х		Continuously				
Concomitant procedures	Х		Continuously				
Adverse events	Х	Continuously			X ⁷		
Subsequent cancer therapy							Х
Survival status							Х

¹ if clinically indicated. Consult a specialist if clinically abnormal and exclude any immune-related myocarditis.

² Full examination is required at baseline and end of treatment. Focused clinical examination shall prevail throughout the course of treatment.

³ Body height will only be measured at screening.

⁴ Full blood count including blood differential test will be performed at baseline, after start of treatment (V2) and further indicated time points throughout treatment and at end of study.

⁵ Sodium, potassium, calcium, magnesium, phosphate, AST, ALT, PTT/INR, LDH, total bilirubin, creatinine, creatinine clearance, albumin, tumor marker CEA, Cyfra 21-1

⁶ To be done at baseline and 3 weeks after start of treatment (V2) and further indicated time points throughout treatment and at end of study. If rising TSH is detected, a full assessment of fT3 and fT4 shall be performed and signs of hormone depletion shall be monitored clinically.

⁷ Follow-up of ongoing SAEs until resolution or stabilization. Serious adverse events are recorded until 90 days after last dose of IMP or for 6 weeks after surgery if the subject initiated new anticancer therapy (e.g. radiochemotherapy). Pregnancies occurring in a study subject are recorded from time of signed informed consent until 120 days after last dose of IMP.

⁸ Repeat assessment if SCR assessment is older than 7 days.

⁹ Post-op. tumor regression grading.

Safety reporting contact information (SAE / Pregnancy)

In the case of a serious adverse event (SAE) or pregnancy safety desk must be contacted within 24 hours.

Contact details for safety reporting are provided in the Investigator Site File.

The safety desk will inform MSD Germany Pharmacovigilance (Email:

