5.2 Study Procedures

5.2.1 Screening Procedures (day -28 to 0)

NOTE: Any routine procedure which is performed during the screening window may be used as a screening assessment in this trial. Documentation of any screening procedure in the eCRF can only be performed after informed consent of the patient. All patients will be screened and screening procedures performed within 28 days prior to start of study treatment include the following:

Signed Informed ConsentObtained prior to any study specific assessment

AIO-Studien-gGmbH

Demographics and medical	○ Age, gender, race
history	 Tumor diagnosis
	 Previous and concurrent relevant diseases
	 Previous treatments
	 Tobacco consumption in pack years
Tumor measurement	See section 5.1.1
according to RECIST 1.1	
(CT or MRI)	
Tumor assessments	Whole body PET-CT and MRI brain scans (or CT
CT or MRI	brain if MRI is not feasible) are required.
Cardiac evaluation	12-lead ECG
Physical examination and	 Physical examination
vital signs	 Body height, weight
	 Vital signs measurements will include body
	temperature, pulse and blood pressure
ECOG performance status	See Appendix 1 – ECOG Performance Status
Serum pregnancy test	A serum pregnancy test will be performed in pre-
	menopausal women and women who are
	menopausal for < 2 years. In case the sampling
	date for serum pregnancy testing exceeds 7 days
	before treatment start, a urine test is required for
	confirmation of the absence of pregnancy.
Lung function	Body plethysmography / blood gas analysis,
	diffusion capacity
Hematology	Hemoglobin, erythrocytes, platelets, leukocytes,
	absolute neutrophils (ANC), basophils, eosinophils,
	lymphocytes, monocytes
Clinical chemistry	Sodium, potassium, calcium, magnesium, albumin
	phosphate, AST, ALT, PTT/INR, LDH, total
	bilirubin, creatinine, creatinine clearance (see
	section 18.4 Appendix 4), TSH
tumor marker	CEA, Cyfra 21-1

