5.2.2 Treatment Phase

For V1 no particular assessments are required. However, the following assessments need to be repeated if the Screening assessment is older than 7 days measured from first dose of IMP: Hematology, pregnancy test, clinical chemistry, coagulation, vital signs. ConMed and AE documentation may need to be updated if required.

During treatment phase the following assessments and procedures will be performed for V2 unless a different time point is mentioned specifically:

Cardiac evaluation	12-lead ECG, transthoracic echocardiogram (TTE)
	if clinically indicated
Physical examinations and	Physical examination
vital signs	Body weight, BSA
	Vital signs measurements will include body
	temperature, pulse and blood pressure
ECOG performance status	Day 1 of each immunotherapy cycle, see

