	Appendix 1 – ECOG Performance Status
Pregnancy test	During treatment phase the pregnancy test should
	be repeated if the investigator considers it
	necessary. A serum or urine pregnancy test will be
	performed in pre-menopausal women and women
	who are menopausal for < 2 years.
Hematology	Hemoglobin, erythrocytes, platelets, leukocytes,
	absolute neutrophils (ANC), basophils, eosinophils,
	lymphocytes, monocytes
Clinical chemistry +	Sodium, potassium, calcium, magnesium,
coagulation	phosphate, AST, ALT, PTT/INR, LDH, total bilirubin,
	creatinine, creatinine clearance (see section 18.4

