7.6.6 Contraception and Pregnancy

Pembrolizumab may have adverse effects on a fetus in utero. Furthermore, it is not known if pembrolizumab has transient adverse effects on the composition of sperm. For this trial, male subjects will be considered to be of non-reproductive potential if they have azoospermia (whether due to having had a vasectomy or due to an underlying medical condition).

Female subjects will be considered of non-reproductive potential if they are either:

(1) postmenopausal (defined as at least 12 months with no menses without an alternative medical cause; in women < 45 years of age a high follicle stimulating hormone (FSH) level in the postmenopausal range may be used to confirm a post-menopausal state in women not using hormonal contraception or hormonal replacement therapy. In the absence of 12 months of amenorrhea, a single FSH measurement is insufficient.);

OR

(2) have had a hysterectomy and/or bilateral oophorectomy, bilateral salpingectomy or bilateral tubal ligation/occlusion, at least 6 weeks prior to screening;

OR

(3) has a congenital or acquired condition that prevents childbearing.

Female and male subjects of reproductive potential must agree to avoid becoming pregnant or impregnating a partner, respectively, while receiving study drug and for 120 days after the last dose of study drug by complying with one of the following:

(1) practice abstinence[†] from heterosexual activity;

OR

(2) use (or have their partner use) acceptable contraception during heterosexual activity.

Acceptable methods of contraception are[‡]:

Single method (one of the following is acceptable):

- intrauterine device (IUD)
- vasectomy of a female subject's male partner
- contraceptive rod implanted into the skin

Combination method (requires use of two of the following):

- diaphragm with spermicide (cannot be used in conjunction with cervical cap/spermicide)
- cervical cap with spermicide (nulliparous women only)
- contraceptive sponge (nulliparous women only)
- male condom or female condom (cannot be used together)

 hormonal contraceptive: oral contraceptive pill (estrogen/progestin pill or progestin-only pill), contraceptive skin patch, vaginal contraceptive ring, or subcutaneous contraceptive injection

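### The 72-hour pregnancy-test window in inclusion criterion 9 is not carried into the visit instructions, which ask for a repeat only after 7 days

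*Protocol*

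**What the plan says.** **Eligibility.** Protocol section 4.2, inclusion criterion 9, says a woman of childbearing potential should have a "negative urine or serum pregnancy within 72 hours prior to receiving the first dose of study medication". The synopsis gives the same window. Exclusion criterion 19 separately requires a negative serum test at screening, with no time limit relative to dosing. Section 5 says patients who do not satisfy the criteria are not to be enrolled.

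**Visit instructions.** Screening runs from Day -28 to Day 0, and dose 1 is given at V1 on Day 1.

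- The schedule marks the pregnancy test at screening and, conditionally, at V1. Footnote 8 sets the condition: "Repeat assessment if SCR assessment is older than 7 days". The SAP reproduces this footnote in section 1.5.
- Section 5.2.1 asks for a confirmatory urine test where the sampling "date for serum pregnancy testing exceeds 7 days" before treatment start.
- Section 5.2.2 requires nothing at V1 by default. It then says that "the following assessments need to be repeated if the Screening assessment is older than 7 days measured from first dose of IMP", and its list includes the pregnancy test.

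**After dose 1.** The schedule shows no pregnancy test at V2. Section 5.2.2 says the test should "be repeated if the investigator considers it" necessary. At the pre-surgical visit (5.2.3), after both doses, the test is done only if clinically indicated.

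**The concern.** The eligibility list and the visit instructions give different limits for the same test, and the visit instructions are the looser. A site working from the schedule and section 5.2 can dose a woman whose last negative test is 4 to 7 days old, see no instruction to repeat it, and still have treated someone outside criterion 9. Nothing at V1 prompts a second look: the schedule places the inclusion/exclusion check at screening only, and SAP section 2.11.1 defines enrolment by an eligibility answer given at screening.

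What is at stake is participant protection and avoidable eligibility deviations. Section 7.6.6 states "Pembrolizumab may have adverse effects on a fetus in utero". Contraception is required, and pregnancy is a reason for removal from treatment (5.3), but removal depends on the pregnancy being found. With no scheduled test at V2, the test before dose 1 is the last one the schedule calls for before either dose.

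The analysis is hardly touched. SAP section 2.9 counts an inclusion violation as major only if it has a relevant effect on efficacy, so a missed 72-hour window is unlikely to alter the per-protocol set.

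**Working it through.** The plan gives no figure to reproduce here. The check compares the stated windows and then sizes the gap under stated assumptions.

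**Inputs from the protocol**

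- Eligibility window: 72 h before the first dose (inclusion criterion 9).
- Repeat trigger: screening test older than 7 days (footnote 8, 5.2.1, 5.2.2).
- Screening: Day -28 to Day 0, which is 29 days. Dose 1: Day 1.

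**Width of the gap**

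7 × 24 h = 168 h; 168 h - 72 h = 96 h, or 4 days.

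**Where it falls, in whole days, with dosing on Day 1**

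| Day of last test | Age at dose 1 | Repeat triggered at 7 days? | Within 72 h? |
|---|---|---|---|
| -28 to -7 (22 days) | 29 to 8 days | Yes | No, unless the repeat is |
| -6 to -3 (4 days) | 7 to 4 days | No | No |
| -2 to 0 (3 days) | 3 to 1 days | No | Yes |

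22 + 4 + 3 = 29. The middle row is the gap. For example, a negative serum test on Day -5 meets exclusion criterion 19 and triggers no repeat, but is 6 days old at dose 1.

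The first row is not fully secure either. Section 5.2.1 asks for a confirmatory urine test but does not say how close to dosing it must be.

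**Expected size**

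Two assumptions are needed, because the documents give neither figure: test days are spread evenly over screening, and n = 0 to 3 of the 30 patients are women of childbearing potential.

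- Share of screening days in the gap: 4/29 = 13.8%.
- Expected number affected: n × 4/29.
- Chance of at least one: 1 - (25/29)^n.

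| n | Expected number | Chance of at least one |
|---|---|---|
| 0 | 0 | 0% |
| 1 | 0.14 | 14% |
| 2 | 0.28 | 26% |
| 3 | 0.41 | 36% |

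The even spread drives these results. If the centre habitually tested on Day -6 to Day -3, all n women (0 to 3) would be affected. If it habitually tested on Day -2 to Day 0, none would be. These figures count women outside the 72-hour window, not pregnancies.

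**After the correction**

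If a repeat were triggered whenever the last test is older than 72 h at dose 1, the uncovered interval would fall from 96 h to 0.

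**The case against.** The strongest reply is that the rules are cumulative. The 7-day trigger is a minimum and nothing in it waives criterion 9. A centre that applies the whole protocol will test within 72 hours and break no visit instruction. That is right, and it limits the point: what is missing is a prompt. It does not remove the point, because the visit instructions are what staff follow on the day, and they indicate that a test 4 to 7 days old needs no repeat.

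Second, criterion 9 says the woman should have the test, while its contraception duty and exclusion criterion 19 use must. The wording is softer, but it stands inside a numbered inclusion criterion and section 5 bars patients who do not meet the criteria. If the 72 hours are only advisory, the protocol should say so. Either reading needs a text change.

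Third, the pregnancy-test row in section 5.2.2 goes on to say that a serum or urine test will be performed in premenopausal and recently menopausal women. Read alone, that could require a test at V2. Since it follows the sentence leaving repeats to the investigator, and the schedule shows no V2 test, it more naturally describes the type of test and who receives it. The row is still not perfectly clear, and in any case a V2 test would come after dose 1.

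Fourth, a woman in the gap already has a negative serum test no more than 7 days old and has agreed to contraception. Nothing in the documents shows how many pregnancies a later urine test would add. This stands, and no harm rate is claimed here.

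**Conclusion.** The inconsistency is real. Criterion 9 sets 72 hours, three places in the protocol and the SAP copy of the schedule work to 7 days, and no text reconciles them. The 96-hour gap follows directly from the stated windows and needs no assumption.

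Its practical size is small: 0 to 0.41 women expected, and at most a 36% chance of at least one, under an even spread of test days and 0 to 3 women of childbearing potential. Concentrated testing on Day -6 to Day -3 would raise the number to 0 to 3. No efficacy or safety estimate depends on it. It should still be corrected, because it concerns a fetal-safety check that the protocol itself asks for. Version 5.0 is dated September 2020 and plans the last patient in for Q2/2021, so enrolment under this text was still expected.

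**What to change.** Keep the 72-hour window and bring the visit instructions into line with it:

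1. Give the V1 pregnancy-test cell in the schedule its own footnote: *Repeat if the last test is older than 72 hours before first dose; result must be negative before dosing.* This also settles the timing of the repeat when the screening test is more than 7 days old.
2. Change the 7-day wording for the pregnancy test to the same rule in sections 5.2.1 and 5.2.2.
3. Carry the footnote into the schedule in SAP section 1.5, so that the copy matches. This directs no testing and is for consistency only.
4. Leave the 7-day rule as it is for hematology, coagulation, clinical chemistry and vital signs.

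The cost is one footnote, its SAP copy and two wording changes, made through a protocol amendment as section 12 requires. For participants it means one extra urine test for a few women, which criterion 9 already calls for.
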